10 STUDY PROCEDURES

10.1. PRE-PROCEDURE EVALUATION

Patients will be consented for the study in either the inpatient or outpatient setting. The following tests and procedures will occur before the ablation as a routine part of pre-procedural medical assessment:

- Recording of patient medical history (including details of previous ablation)
- Recording of patient AF/AT recurrences
- Recording medication history (including all anti-arrhythmic drugs used and duration of use)
- Obtain β -HCG in females of child bearing age the morning of the procedure as per usual clinical practice
- Baseline assessment of arrhythmia burden and type: Office/inpatient records, ICD interrogation report
- Collect any pre-procedural echocardiograms
- Baseline laboratory, including complete blood count, standard electrolyte panel, renal function
- Baseline TTE to assess any adverse conditions.
- Consent must be obtained before the procedure.

10.2 PRE-PROCEDURE MEDICATION MANAGEMENT

It will be recommended that all subjects take therapeutic doses of anticoagulation for at least 3 weeks prior to their catheter ablation procedure. For those who are not taking anticoagulation for this length of time prior to their procedure, a pre-procedural transesophageal echocardiogram will be recommended if the subject presents in atrial fibrillation and has CHA2DS2-VASc score ≥ 1 .

For subjects who are taking warfarin at the time of the ablation, it will be continued uninterrupted through the procedure. For subjects who are taking novel oral anticoagulants (NOACs) with twice daily dosing (dabigatran, apixaban), the morning dose on the day of the ablation will be held, and the NOAC will be resumed the evening after the procedure at the primary operator's discretion. For subjects who are taking NOACs with once daily dosing (rivaroxaban), the last dose will be the night prior to the procedure, and the NOAC will be resumed the evening after the procedure at the primary operator's discretion.

Every effort will be made to discontinue AADs prior to ablation.

10.3 PROCEDURAL DETAILS

- Patients will be brought to the electrophysiology laboratory in a fasting state
- Patients will undergo ECG to determine rhythm – i.e. Sinus rhythm v Atrial fibrillation
- Patients will undergo electrophysiology study using a mapping system and ablation as per standard practice. Placement of trimmed patches will be placed in standardized locations.
- The AF ablation procedure will be performed using any of the following marketed catheters: (Note: the first 3 catheters listed below are FDA approved for the treatment of paroxysmal

atrial fibrillation but not persistent The FlexAbility is only approved for treatment of typical atrial flutter.)

- Biosense-Webster Smart Touch SF
- Biosense-Webster Thermocool SF
- St. Jude Medical TactiCath Quartz
- St. Jude Therapy FlexAbility
- Intraprocedural anticoagulation will be administered with intravenous heparin, with target ACT levels ≥ 350 sec during any period in which catheters are positioned in the left atrium.
- For all patients, the initial ablation lesion set will consist of pulmonary vein isolation, assessed by entrance block during electrode recordings in the PV and by exit block during pacing from the PV.
- It will be suggested to operators that energy and duration of any RF lesions delivered either during PV isolation or subsequent ablation of drivers should be titrated to a goal tissue impedance drop ≥ 10 ohms from baseline during each lesion. Additionally, acute elimination of all local electrograms at ablation sites will be encouraged.

Presenting rhythm - Sinus

- AF is induced by pacing
- Electro anatomic maps of right and left atria are created and PV isolation is assessed with multielectrode mapping catheter.
- Once this occurs - **Map_{inducedAF}** is obtained using the CMA software running on the laptop adjacent to the 3D Mapping System.
- Ablation of drivers can be initiated in chamber with faster CL or with greater number of identified drivers
- Drivers can be addressed in order of importance as suggested by maps.
- Periodic reassessment of TCL in LAA and RAA to be done to help direct operator to chamber of interest- e.g. if there is significant gradient between RAA and LAA such that RAA is faster then drivers can be pursued in RAA prior to completion of all driver regions of LA
- All drivers are to be sequentially ablated or isolated using the St Jude Ensite system to navigate ablation catheter to the anatomic region identified by the AF mapping as a potential driver domain, assessing the local electrograms via St. Jude Ensite system and delivering ablation via St. Jude ablation catheter. If rhythm is still not organized then ablation sites are visited again to ensure adequate ablation.
- Then, Re-assess rhythm
- If AF persists, Real time electrogram processing mapping should be repeated (**Map_{Re1,2,...}**) and additional driver regions targeted.
- If the rhythm organizes to an atrial tachycardia, it should be targeted for ablation
- If rhythm is still in AF despite elimination of all drivers based on repeated Maps or if no drivers are localized- the patient will be cardioverted to sinus rhythm (Number of remaps is at the discretion of operator)

- If during AF or AT ablation- the patient reverts to sinus rhythm- ablation is complete at that site as per operator definition of sufficient ablation. Additional drivers localized during mapping will also be targeted despite sinus rhythm
- Empiric ablation (CFAE or linear ablation) is not permitted

Presenting rhythm - Atrial fibrillation

- Electro anatomic maps of right and left atria are created and PV isolation is assessed with multielectrode mapping catheter.
- **Map_{spontAF}** will be acquired CMA software running on the laptop adjacent to the 3D Mapping System.
- Prior to ablation- LAA and RAA cycle length are to be measured over 10 beats.
- Ablation of drivers can be initiated in chamber with faster CL or with greater number of identified drivers
- Drivers can be addressed in order of importance as suggested by maps.
- Periodic reassessment of TCL in LAA and RAA to be done to help direct operator to chamber of interest- e.g. if there is significant gradient between RAA and LAA such that RAA is faster then drivers can be pursued in RAA prior to completion of all driver regions of LA
- All drivers are to be sequentially ablated or isolated using the St Jude Ensite system to navigate ablation catheter to the anatomic region identified by the AF mapping as a potential driver domain, assessing the local electrograms via St. Jude Ensite system and delivering ablation via St. Jude ablation catheter. If rhythm is still not organized then ablation sites are visited again to ensure adequate ablation.
- Then, re-assess rhythm
- If AF persists, real time electrogram processing mapping should be repeated (**Map_{Re1,2,...}**) and additional driver regions targeted. (previous driver regions may be revisited to ensure elimination of complex EGMs)
- If the rhythm organizes to atrial tachycardia this will be ablated and if rhythm converts to sinus – then procedure is deemed complete. Additional drivers are to be targeted based on **Map_{Re1,2}**
- If presenting rhythm is AF- and **Map_{spontAF}** has been acquired; induced AF map based driver ablation is not required unless this occurs spontaneously
- Empiric ablation (CFAE or linear ablation) is not permitted

10.4 POST-PROCEDURE

10.4.1 POST-PROCEDURE FOLLOW UP

- Discharge criteria decisions will be made at the discretion of the primary operator per current guidelines.
- Medication and adverse event review will be performed prior to discharge.
- Complications including vascular, stroke, heart failure, pericardial effusion, tamponade, bleeding, and death will be documented.
- The post ablation blanking period will last 3 months only - any AAD is permitted but should be stopped by 8 weeks after the study procedure
- The total number of episodes of post-blanking AT or AF episode > 30 seconds will be recorded

- Patients will undergo continuous 7 day ambulatory monitoring at 3, 6 and 12 months
- Review of medications and adverse events will be performed at the 3, 6 and 12 month follow up
- At any time during the follow-up period, patients will be allowed a second ablation procedure using the CMA software should recurrence of AF occur. Data from the second procedure will be recorded.

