Primary Endpoints:	
 1. Acute Procedural Outcome Analysis: after performing procedures on the 65 patients 2. Clinical Outcome Analysis - Freedom from recurrent AF after one

	
procedure at 12 months.
 
3. Clinical Outcome Analysis – Freedom of recurrent AF after two procedures at 12 months.

Additional Endpoints:	
1. Clinical Outcome Analysis – Freedom from recurrent AT after one procedure at 12 months.
 
2. Clinical Outcome Analysis – Freedom from recurrent AT after two procedures at 12 months.
 
3. Total duration of RF ablation/Fluoro time/exposure/ procedure time
 
4. Procedure-related adverse events
 
5. Major Adverse Cardiac Events (MACE)
 
6. Serious Adverse Events

Follow-Up	
1. Post-Ablation blanking period = 3 months
 
2. AAD use during blanking: Any AAD is permitted, but should be stopped by 8 weeks post-procedure.
 
3. Any documented post-blanking AF episode > 30 seconds would be considered as a failure
 
4. Patients will undergo continuous 7-14 day ambulatory monitoring at 3, 6 and 12 months
 
5. A second ablation procedure using the CMA software is allowed should a patient have recurrence of AF at any time during the 1 year follow-up period.

Principal Investigator:	
[name] , M.D. Icahn School of Medicine at Mount Sinai [name]

Site, Monitoring, and Data Management Center	
Electrophysiology Clinical Research Group Icahn School of Medicine at Mount Sinai [name]

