6 ENDPOINTS

6.1 Primary Endpoint

Primary Endpoints:	
1. Acute Procedural Outcomes as defined by termination of Atrial Fibrillation into NSR or AT > 5min.2. Clinical Outcome Analysis - Freedom from recurrent AF after one procedure at 12 months.3. Clinical outcome Analysis – Freedom from recurrent AF after two procedures at 12 months.
Additional Endpoints:	
1. Clinical outcome Analysis – Freedom from recurrent AT after one procedure at 12 months.2. Clinical outcome Analysis – Freedom from recurrent AT after two procedures at 12 months.3. Total duration of RF ablation/Fluoro time/exposure/procedure time4. Procedure-related adverse events5. Major Adverse Cardiac Events (MACE)6. Serious Adverse Events

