17 DATA ANALYSIS

This clinical study is a proof of concept study intended to assess the feasibility of the study mapping system. Baseline clinical characteristics (e.g. age, gender, renal function) and procedural characteristics (e.g. surface intracardiac electrogram and imaging findings) of the patients will be collected and analyzed.

Descriptive statistical data will be used to draw up the characteristics of subjects at the time of enrollment (demographics, baseline data). Quantitative parameters will be described using the following summary descriptive statistics: mean, standard deviation, median, and minimum and maximum values. Qualitative parameters will be described overall using frequencies and percentages. Percentages will be calculated on the number of non-missing observations. In all cases, the number of missing values will be specified.

Wilcoxon's test or Student's test for pairwise comparisons will be used, depending on the normality of the distribution, to study evolution in time.

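### AF freedom at 12 months is scored without regard to antiarrhythmic drug use, so patients who miss the week-8 stop or restart can still be counted AF-free

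*Combined protocol and SAP*

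**What the plan says.** Section 6.1 lists two 12-month clinical outcomes among the primary endpoints: "Freedom from recurrent AF after one procedure at 12 months" and "Freedom from recurrent AF after two procedures at 12 months". Neither mentions antiarrhythmic drugs. Freedom from AT after one and after two procedures appears only under the additional endpoints.

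The one scoring rule is in the Follow-Up row of the Protocol Summary: "Any documented post-blanking AF episode > 30 seconds would be considered as a failure". The same row sets a 3-month blanking period and the drug rule, "Any AAD is permitted, but should be stopped by 8 weeks post-procedure". Sections 10.4.1 and 10.4.2 repeat the drug rule: "any AAD is permitted but should be stopped by 8 weeks after the study procedure". Before the procedure, section 10.2 says "Every effort will be made to discontinue AADs prior to ablation".

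Drug use is looked at during follow-up: "Review of medications and adverse events will be performed at the 3, 6 and 12 month follow up" (section 10.4.1), and Table 1 in section 5 schedules medications at the same visits. Section 17 is descriptive. For categorical outcomes it says "Qualitative parameters will be described overall using frequencies and percentages", and it gives no rule for drug use after week 8.

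**The concern.** The week-8 stop shows that outcomes were meant to be assessed off drug, but neither the endpoint nor the analysis carries that intention through. Two kinds of patient fall in the gap: those who never stop, and those who restart for something the failure rule does not count. AT is the obvious example, since it is not a primary failure. AF inside the blanking period is another.

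At stake is what the 12-month rate means. With no control arm, the data cannot show how much of the AF freedom is due to a drug. Section 3 sets the need for the strategy against a cited 59% for PV isolation alone, so readers will put this study's rate beside such figures and need to know drug status to do so. If the handling is chosen after un-blinded results are in hand, the choice is post hoc.

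**Working it through.** **The plan's own figure.** There is none to reproduce. Section 8 sets the 65 patients by feasibility, and no expected success rate or drug-use share is given.

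**Step 1: apply the written rules to each kind of patient (one-procedure endpoint).**

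| Patient | Documented post-blanking AF > 30 s? | Scored |
|---|---|---|
| Stops by week 8, no AF | No | AF-free, off drug |
| Does not stop, no AF | No | AF-free, on drug |
| Restarts for AT or another reason, no post-blanking AF | No | AF-free, on drug |
| Restarts because of documented post-blanking AF | Yes | Failure already |

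The second and third rows are the gap. The stop (8 weeks) comes before the blanking period ends (3 months, about 13 weeks), so a patient who follows the rule and does not restart never enters it.

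**Step 2: two-procedure endpoint.** Section 10.4.1 allows a second ablation at any time in follow-up. The documents do not say whether the 8-week allowance runs again from that procedure. If it does, a patient whose second procedure falls in the last 8 weeks before month 12 could be on drug at month 12, within the rule, and scored AF-free.

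**Step 3: size, under stated assumptions.** Let s be AF freedom regardless of drug use and q the share of AF-free patients on drug after week 8. Then:

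- off-drug rate = s × (1 − q)
- gap between the two definitions = s × q

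Inputs: s = 0.59 is borrowed from section 3 (PV isolation alone, another trial, 18 months); s = 0.70 is assumed; q = 0.10 to 0.30 is assumed.

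| s | q = 0.10 | q = 0.20 | q = 0.30 |
|---|---|---|---|
| 0.59 | 53.1% (gap 5.9) | 47.2% (gap 11.8) | 41.3% (gap 17.7) |
| 0.70 | 63.0% (gap 7.0) | 56.0% (gap 14.0) | 49.0% (gap 21.0) |

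The range is 41-63% off drug, 6 to 21 points below s.

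**Step 4: compare with the precision of the study.** Section 9.1 puts the map-guided cohort at potentially patients 16-65, so about 50. Assume 30/50 AF-free (60%; exact 95% CI 45-74%, half-width about 14 points). If 3, 6 or 9 of the 30 were on drug (q = 0.10, 0.20, 0.30), the off-drug counts are:

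- 27/50 = 54% (CI 39-68%)
- 24/50 = 48% (CI 34-63%)
- 21/50 = 42% (CI 28-57%)

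The gaps are 6, 12 and 18 points. At q = 0.20 the choice of definition moves the figure nearly as much as sampling error does; at 0.30 it moves it more.

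**Step 5: what the gap measures.** Some AF-free patients on drug would have been AF-free without it. If r is that fraction, drug-caused inflation is s × q × (1 − r). It equals the full gap only when r = 0, so s × q is an upper bound for a given q.

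**The case against.** The strongest reply is that the design already deals with this. The stop is written three times and comes before scoring starts, drugs are also to be withdrawn before ablation, and the investigator is responsible for adherence. Reading the word should as permission to continue is weak, because section 10.3 uses it for core procedural steps too. Restarts prompted by documented post-blanking AF are already one-procedure failures, and AT recurrence has its own endpoints. All of this stands. It narrows the gap to departures from the rule and restarts for other reasons, but it does not say how those patients are scored.

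A second reply is that this is a descriptive proof-of-concept study with no hypothesis, comparator or performance goal, and that its objective in section 2 is to identify driver domains. Every patient also gets PV isolation, so the 12-month rate could not isolate map-guided ablation even with everyone off drug. This also stands: no type I error or power is affected, and the acute endpoint is untouched. But section 8 calls the study one of safety and efficacy that yields preliminary estimates, and 12-month AF freedom is listed as primary, so what that rate means is worth settling.

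A third reply is that medications are recorded anyway, so an off-drug rate can be produced at reporting. It probably can, but the definition would then be chosen with the results known.

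**Conclusion.** The point holds as a gap in scoring and analysis. Non-stoppers, and patients who restart for a reason other than documented post-blanking AF, are AF-free under the only failure rule, and no planned analysis separates them. In a single-arm study the rate is then partly a drug effect of unknown size.

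A reader might infer two stronger things. One is that the protocol expressly counts patients on drug as successes. It does not; it is silent, and the result follows only because documented AF is the sole stated failure criterion. The other is that the success rate will be inflated by 6 to 21 points. The documents give no share on drug, and 30% would mean frequent departures from, or restarts after, a stop stated three times. The figures are a difference between two definitions under assumed shares, and an upper bound on drug-caused inflation for those shares. If nearly everyone stops and stays off, the gap is close to zero.

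This is a cheap improvement to interpretability, not a flaw that undermines the study.

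**What to change.** This is a change to scoring and reporting only, with no change to any treatment rule.

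1. Pre-specify each of the two 12-month AF-freedom endpoints twice: regardless of antiarrhythmic drug use, and off antiarrhythmic drugs. For the second, any use after week 8 counts as not meeting the off-drug endpoint.
2. For the two-procedure endpoint, count the 8 weeks from the last procedure for scoring purposes, and list separately any patient still within 8 weeks of a second procedure at month 12.
3. Tabulate antiarrhythmic drug use at 3, 6 and 12 months from the medication review already scheduled.

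The cost is one extra analysis from data already collected, and a second, lower figure to report. One limit remains: visit-based review may miss short courses between visits. Recording antiarrhythmic drug start and stop dates on the case report form would reduce that.

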10.4.2 POST-PROCEDURE MEDICATION MANAGEMENT

- Standard cardiovascular medications are left up to the discretion of the investigator.
- Therapeutic anticoagulation beyond the requisite 2 month post-procedure time point will be at the discretion of the patient's physician.
- The post ablation blanking period will last 3 months only - any AAD is permitted but should be stopped by 8 weeks after the study procedure

11 SAFETY

The local site Principal Investigator will oversee the safety of the study at his/her site. The Data Coordinating Center will provide on-site and remote monitoring to assess safety issues at each site. Additionally, a Data Monitoring Committee will review safety data on a 6 month basis or as needed. A detailed tally of adverse events will be kept and are defined below.

Adverse Events

An adverse event is any undesirable clinical occurrence in a study patient, whether or not it is related to the study intervention. Any condition that was recorded as pre-existing is *not* an adverse event unless there is a change in the nature, severity or degree of the condition.

Serious Adverse Event

Serious adverse events are defined by FDA regulation as any experience that results in a fatality or is life threatening; results in significant or persistent disability; requires or prolongs a hospitalization; results in a congenital anomaly/birth defect; or represents other significant hazards or potentially serious harm to research subjects or others, in the opinion of the investigators. Important medical events that may not result in death, be life-threatening, or require hospitalization may be considered a serious adverse event when, based upon appropriate medical judgment, they may jeopardize the patient and may require medical or surgical intervention to prevent one of the outcomes listed in this definition. Examples of such medical events include bronchospasm requiring intensive treatment in an emergency room or at home, blood dyscrasias, or convulsions that do not result in inpatient hospitalization.

12 RISKS

Patient confidentiality risks associated with any research study are minimal and include: breach of confidentiality and loss of personal data.

Potential Risks Associated with AF Ablation

- Death: End of Life
- Stroke (also called Cardiovascular Accident or CVA): may cause an interruption in the blood supply to a part of the brain
- Pericarditis: inflammation may occur in the outer lining of the heart (<1%).
- Cardiac perforation causing pleural effusion or tamponade: fluid build-up around the heart. A hole in your heart wall (*perforation*) could result in bleeding into the sac, called the pericardium, which surrounds your heart (*cardiac tamponade*). This may be treated by insertion of a needle, through your chest wall, into the sac and removal of the blood. This type of hole sometimes requires surgical repair
- Heart Valve injury (also called Valvular Damage/Insufficiency): an injury to a valve structure resulting in a loss and/or worsening of function (e.g., worsening of regurgitation score or prolapse) (<1%).
- Acute Pulmonary edema: fluid accumulation (build-up) in the lungs (<1%).
- Pulmonary embolism: blockage of a pulmonary artery; a blood clot from a vein may get stuck in the lungs. This is usually treated with drugs (<1%).
- Vascular access complications: an obstruction or perforation or damage to the vascular (blood vessel) system (2%).
- Arterial/venous thrombus: clot formation in the artery or vein (1.5%).
- AV fistula: an abnormal passageway (such as a hole) between an artery and a vein; this may allow blood to go between the arteries and veins and not through the entire body. This may cause some part of the body to not receive the usual amount of blood. This may heal on its own, but may require surgical repair (1.5%).
- Catheter insertion site hematoma: bleeding or bruising from the site of catheter placement. This may go away without treatment, but may require manual compression or surgical repair. If excessive bleeding at the site of the catheter placement continues, this could result in anemia requiring medical intervention (2%).
- Hypoxia: reduced oxygen supply to tissue (<1%).
- Infection, Localized or systemic: an infection may occur anywhere an incision or cut is made during the procedure (<1%).
- Peripheral venous thrombosis: blood clots in the vein (<1%).
- Phrenic nerve damage: damage to the nerve that controls the diaphragm and may affect your breathing. Symptoms may be temporary but in some cases can be permanent (respiratory arrest) (<1%).
- Pneumonia: infection of lungs or gathering of fluid in the lungs (<1%).
- Pseudoaneurysm: development of a false pouch in the vessel wall. This can be caused by movement of catheters in the blood vessels. This may heal on its own, but sometimes need surgical repair (<1%).
- Radiation injury resulting in dermatitis (skin burns): (<1%).
- Respiratory failure: damage to breathing that can be permanent (respiratory arrest) (<1%).
- Radiation exposure during the fluoroscopic imaging of the catheters during ablation: this may slightly increase the lifetime risk of developing a fatal malignancy or a genetic defect in offspring (<1%).
- Fluid overload: excessive fluid built up could result in pulmonary (lung) edema; congestive heart failure (CHF) may occur or may be exacerbated (worsened) due to delivery of sterile salt water (saline) during the procedure (these risks are specific to open irrigated ablation catheters) (1.5%).

Potential Risks Associated with investigational mapping system:

- The additional investigational mapping done for this study may cause patients to have a prolonged procedure time. The patients may be exposed to additional anesthesia as a

- result of this prolonged procedure time.
- Potential harms of a more extensive bi-atrial lesion set over PV isolation include prolonged procedure time and atrial stunning.

